#### **7.2.1.1.2 Dose Modification and Toxicity Management for Immune-Related AEs Associated with Pembrolizumab and Immuno-oncology (IO) combination partners**

AEs associated with pembrolizumab or IO/IO combination exposure, , may represent an immunologic etiology. These immune-related AEs (irAEs) may occur shortly after the first dose or several months after the last dose of pembrolizumab or combination treatment and may affect more than one body system simultaneously. Therefore, early recognition and initiation of treatment is critical to reduce complications. Based on existing clinical study data, most irAEs were reversible and could be managed with interruptions of pembrolizumab or combination treatment, administration of corticosteroids and/or other supportive care. For suspected irAEs, ensure adequate evaluation to confirm etiology or exclude other causes. Additional procedures or tests such as bronchoscopy, endoscopy, skin biopsy may be included as part of the evaluation. Based on the severity of irAEs, withhold or permanently discontinue pembrolizumab or combination treatment and administer corticosteroids. Dose modification and toxicity management guidelines for irAEs associated with pembrolizumab are provided in Table 3 and Table 6.

**Note:** The treatment guidelines are intended to be applied when the investigator determines the events to be related to pembrolizumab. If after the evaluation the event is determined not to be related to pembrolizumab, the investigator does not need to follow the treatment guidance.

**Table 3 - Dose modification and toxicity management guidelines for immune-related AEs associated with pembrolizumab and IO combination partners**

General instructions:				
Immune-related AEs	Toxicity grade or conditions (CTCAE v5.0)	Action taken to pembrolizumab	irAE management with corticosteroid and/or other therapies	Monitor and follow-up
Pneumonitis	Grade 2	Withhold	
 
Administer corticosteroids (initial dose of 1-2 mg/kg prednisone or equivalent) followed by taper
 
Add prophylactic antibiotics for opportunistic
 
	
 
Monitor participants for signs and symptoms of pneumonitis
 
Evaluate participants with suspected pneumonitis with radiographic imaging and initiate corticosteroid treatment
 

	Recurrent Grade 2, Grade 3 or 4	Permanently discontinue		

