AE(s)=adverse event(s); ALT= alanine aminotransferase; AST=aspartate aminotransferase; CTCAE=Common Terminology Criteria for Adverse Events; DRESS=Drug Rash with Eosinophilia and Systemic Symptom; GI=gastrointestinal; IO=immuno-oncology; ir=immune related; IV=intravenous; SJS=Stevens-Johnson Syndrome; T1DM=type 1 diabetes mellitus; TEN=Toxic Epidermal Necrolysis; ULN=upper limit of normal.				
Note: Non-irAE will be managed as appropriate, following clinical practice recommendations.				
A AST/ALT: >3.0 to 5.0 x ULN if baseline normal; >3.0 to 5.0 x baseline, if baseline abnormal; bilirubin: >1.5 to 3.0 x ULN if baseline normal; >1.5 to 3.0 x baseline if baseline abnormal				
B AST/ALT: >5.0 to 20.0 x ULN, if baseline normal; >5.0 to 20.0 x baseline, if baseline abnormal; bilirubin: >3.0 to 10.0 x ULN if baseline normal; >3.0 to 10.0 x baseline if baseline abnormal				
C AST/ALT: >20.0 x ULN, if baseline normal; >20.0 x baseline, if baseline abnormal; bilirubin: >10.0 x ULN if baseline normal; >10.0 x baseline if baseline abnormal				
D The decision to withhold or permanently discontinue pembrolizumab is at the discretion of the investigator or treating physician. If control achieved or $\leq$ Grade 2, pembrolizumab may be resumed.				
E Events that require discontinuation include, but are not limited to: encephalitis and other clinically important irAEs.				

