Grades 3 or 4 Grade 3: Prolonged (i.e., not rapidly responsive to symptomatic medication and/or brief interruption of infusion); recurrence of symptoms following initial improvement; hospitalization indicated for other clinical sequelae (e.g., renal impairment, pulmonary infiltrates) Grade 4: Life-threatening; pressor or ventilatory support indicated	
Stop Infusion.
 
Additional appropriate medical therapy may include but is not limited to: Epinephrine**, IV fluids, Antihistamines, NSAIDs, Acetaminophen, Narcotics, Oxygen, Pressors, Corticosteroids
 
Increase monitoring of vital signs as medically indicated until the participant is deemed medically stable in the opinion of the investigator.
 
Hospitalization may be indicated.
 
**In cases of anaphylaxis, epinephrine should be used immediately.
 
Participant is permanently discontinued from further study drug treatment.
	No subsequent dosing

Appropriate resuscitation equipment should be available at the bedside and a physician readily available during the period of drug administration.
 
For further information, please refer to the Common Terminology Criteria for Adverse Events v5.0 (CTCAE) at http://ctep.cancer.gov
		

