## 7.4 Subject Withdrawal/Discontinuation Criteria

Subjects may withdraw consent at any time for any reason or be removed from the trial at the discretion of the Sponsor-Investigator for any reason. In addition, a subject may be withdrawn by the Sub-Investigator or the Sponsor-Investigator if enrollment into the trial is inappropriate, the trial plan is violated, or for administrative and/or other safety reasons. When a subject discontinues/withdraws prior to 90 Day Follow-Up Visit, all applicable activities scheduled for the 90 Day Follow-Up visit should be performed at the time of discontinuation.

A subject will be considered withdrawn and no longer followed if they enroll onto hospice care.

A subject must be discontinued from the trial for any of the following reasons:

- The subject or legal representative (such as a parent or legal guardian) withdraws consent.
- Unacceptable adverse experiences as described in Section 7.2.1.1
- Intercurrent illness that prevents further administration of treatment
- Sponsor-Investigator's decision to withdraw the subject
- The subject has a confirmed positive serum pregnancy test
- Noncompliance with trial treatment or procedure requirements
- The subject is lost to follow-up
- Administrative reasons
- Subject progresses (clinically and/or radiologically) and is no longer a surgical candidate.

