### 7.4.1 Discontinuation of Study Therapy after CR

All subjects will complete the three scheduled pembrolizumab injections prior to the first radiographic assessment of response unless one of the criteria is met in Section 7.4.

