## 7.5 Subject Replacement Strategy

Should any subjects fail to complete at least 2 doses of pembrolizumab and surgery, they will be replaced.

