### **9.3.6 Survival Follow-up**

Disease status and any subsequent anticancer therapy information status will continue to be monitored. Subjects will be contacted by telephone or medical record review every 12 weeks ( $\pm$  2 weeks) after the 30 Day Follow-Up Visit to assess for disease status, recurrence, and survival status until 1 year after initiation of pembrolizumab therapy, death, withdrawal of consent, or the end of the study, whichever occurs first. After the first year, then subjects will be contacted either by telephone or medical record review every 6 months ( $\pm$  1 month) to assess for disease status, recurrence, and survival status until 5 years after initiation of pembrolizumab, death, withdrawal of consent, or the end of the study, whichever comes first.

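### Section 7.4 requires trial exit for toxicities that Section 7.2.1.1 handles only by stopping pembrolizumab; read literally, this could select the necrosis result on toxicity

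*Combined protocol and SAP*

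**What the plan says.** Section 7.4 opens its mandatory list with "A subject must be discontinued from the trial for any of the following reasons", and one item on that list is "Unacceptable adverse experiences as described in Section 7.2.1.1". The same section brings the 90-Day Follow-Up activities forward to the moment of discontinuation when a subject leaves before that visit.

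The section it points to concerns one drug. In Table 3 the relevant column is headed "Action taken to pembrolizumab", and footnote D reads "The decision to withhold or permanently discontinue pembrolizumab is at the discretion of the investigator or treating physician". Table 4, for Grade 3 or 4 infusion reactions, says "Participant is permanently discontinued from further study drug treatment". Neither table mentions leaving the trial.

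Other sections bear on the same subjects:

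- Section 7.4.1 uses the 7.4 list as the exception to completing the drug course: "All subjects will complete the three scheduled pembrolizumab injections prior to the first radiographic assessment of response unless one of the criteria is met".
- Section 9.3 names unacceptable adverse events as one of the points at which therapy ends.
- Section 7.5: "Should any subjects fail to complete at least 2 doses of pembrolizumab and surgery, they will be replaced". Section 7.2.3 also replaces anyone who does not reach surgery, whatever the reason.
- Section 9.3.6 continues survival follow-up "until 5 years after initiation of pembrolizumab, death, withdrawal of consent, or the end of the study, whichever comes first". Footnote 6 of Section 8.1 gives the same four end points.

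**The concern.** One list in 7.4 does two jobs. It states when a subject leaves the trial, and through 7.4.1 it also states when a subject stops pembrolizumab. For consent withdrawal or loss to follow-up the difference hardly matters. For toxicity it does, because the primary endpoint is read on the resection specimen weeks after the last dose.

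If a site follows 7.4 to the letter, a subject who has had at least two doses and stops for toxicity is off the trial before the necrosis result exists. The replacement rules can then restore the count to 26. The loss would not show as a smaller sample. It would show, if at all, as a necrosis rate in subjects selected for having tolerated pembrolizumab. Tolerability is itself a secondary objective (Section 4.2), so these subjects are among the more informative ones. Whether such a subject contributes would depend on which section the site applied.

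**Working it through.** **1. The passages side by side.** Take a subject who has two doses, develops Grade 3 nephritis before the third, finishes radiation and is due for surgery.

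- Table 3: pembrolizumab is permanently stopped. Nothing is said about the trial.
- Section 9.3: therapy ends, if the event counts as unacceptable.
- Section 7.5: with two doses and surgery, the subject is not replaced.
- Section 9.3.6 and footnote 6 of 8.1: none of the end points has been reached, so survival follow-up continues.
- Section 7.4, read literally: the subject leaves the trial now, before surgery, and the 90-Day activities are done now. Footnote 2 of 8.1 places that visit after any scheduled surgery, so the two instructions conflict. The activities in 9.3.4 include neither resection pathology nor response imaging.

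If this subject then has no operation, 7.2.3 and 7.5 require a replacement. If the operation goes ahead as standard care, the specimen exists, but no section says whether a subject discontinued under 7.4 still counts for the primary endpoint.

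**2. The plan's own figure.** Section 10.1 gives 26 subjects, 15% against 40%, a criterion of at least 7 complete necroses, and 94.4% power. By exact binomial:

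- P(X ≥ 7 | n = 26, p = 0.40) = 0.944, which agrees with the plan.
- P(X ≥ 7 | n = 26, p = 0.15) = 0.083. The plan states no alpha; this is the one-sided level that its rule implies.
- Criteria of 6 or 8 would give power of 0.979 or 0.878, so 7 is the criterion behind the stated power.

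**3. Effect of selection with replacement to 26.** The documents give no rate of stopping for toxicity. Let t be the assumed share who exit before surgery and are replaced, q their necrosis rate had they stayed, and 15% the true rate in all enrolled. The rate among those analysed is

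p = (0.15 − t·q) / (1 − t)

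| t | q | p | P(X ≥ 7 of 26) |
|---|---|---|---|
| 0 | – | 0.150 | 8.3% |
| 10% | 0% | 0.15/0.90 = 0.167 | 12.9% |
| 10% | 15% | 0.135/0.90 = 0.150 | 8.3% |
| 10% | 40% | 0.11/0.90 = 0.122 | 3.3% |
| 20% | 0% | 0.15/0.80 = 0.188 | 20.2% |
| 20% | 15% | 0.12/0.80 = 0.150 | 8.3% |
| 20% | 40% | 0.07/0.80 = 0.088 | 0.6% |

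If exit is unrelated to necrosis (q = 15%), nothing changes. Otherwise the error can go either way, and the documents do not indicate which.

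**4. Enrolment.** To end with 26 analysed, about 26/0.90 = 28.9, so 29, must enrol at 10% exit, and 26/0.80 = 32.5, so 33, at 20%.

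**5. What belongs to 7.4 alone.** A subject who stops after one dose is replaced under 7.5 whatever 7.4 says. The effect specific to 7.4 is therefore limited to subjects with at least two doses who leave before surgery. The 10% and 20% rows are upper-end illustrations for that group.

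**The case against.** The best defence is that the protocol, read as a whole, treats the 7.4 toxicity item as a rule for stopping therapy. Sections 9.3 and 7.4.1 support that. In 7.4 itself only hospice enrolment is said to end follow-up. Much data would be collected anyway:

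- Section 9.4.1 follows events above Grade 1 until they settle or new anti-neoplastic therapy begins.
- Section 9.4.2 keeps serious events reportable for 90 days after pembrolizumab stops (30 days if a new anticancer therapy starts sooner), follows all of them to outcome, and keeps events of clinical interest reportable for 120 days.
- Section 3.3 continues monitoring of wound problems and treatment-related toxicity still present at the Wound Care visit, and allows survival status to be taken from records.
- Under Section 3.4 necrosis is read from standard-of-care pathology.

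This stands as far as it goes. A reader might infer from 7.4 that necrosis, wound, late-toxicity and survival data will be lost in these subjects. The documents do not say so; loss is a risk under one reading. A reader might also infer that every permanent-stop row in Table 3 forces trial exit. Section 7.2.1.1 never defines which events are unacceptable, so that too is inference, including for the nephritis example. Nor does it follow that the analysis shrinks below 26: subjects who miss surgery are replaced, and those operated on after two doses have a specimen.

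The defence does not remove the conflict. The hospice sentence does not say what happens after other discontinuations. The toxicity item shares one list and one stated consequence with consent withdrawal and loss to follow-up. That the data may exist is not a rule that they will be used.

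**Conclusion.** The inconsistency is real. Section 7.4 attaches trial exit to events for which 7.2.1.1 prescribes only an action on pembrolizumab, and this does not fit with 7.4.1, 7.5, 9.3, 9.3.6 or footnote 6 of 8.1. The consequence is a possible selection of the primary result on toxicity, hidden by replacement. It is not an established loss of data, and it is not a loss of power through a smaller sample.

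The size cannot be known from the documents. The shift calculated above, from 8.3% to as little as 0.6% or as much as 20.2%, rests on four assumptions: 10% or 20% exit, all exits replaced, a true overall rate of 15%, and an exiting-subject necrosis rate of 40% or 0%. With few such exits, or with necrosis unrelated to toxicity, the effect is small or nil. The point is worth correcting because it touches the primary endpoint and the correction is cheap.

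**What to change.** Reconcile 7.4 with 7.2.1.1, 7.4.1, 7.5, 8.1 footnote 6, 9.3 and 9.3.6 by separating two things: discontinuation of pembrolizumab and withdrawal from the trial. State that:

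- stopping pembrolizumab does not by itself end data collection, so pathology (if surgery occurs), the scheduled visits and survival follow-up continue;
- a subject who stopped pembrolizumab but meets the 7.5 rule, at least two doses and surgery, is counted in the necrosis denominator;
- 7.4.1 refers to discontinuation of pembrolizumab.

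The sponsor should also say which 7.2.1.1 events the 7.4 item means. No toxicity threshold or clinical rule is changed or proposed here; the clinical content of these passages is for the sponsor to settle.

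The cost is a wording amendment and a few visits that are already in the schedule. If stopping the drug does not mean leaving the trial, subjects who meet 7.5 keep their results and the design stays at 26 with 94.4% power.

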### 7.4.1 Discontinuation of Study Therapy after CR

All subjects will complete the three scheduled pembrolizumab injections prior to the first radiographic assessment of response unless one of the criteria is met in Section 7.4.

## 7.5 Subject Replacement Strategy

Should any subjects fail to complete at least 2 doses of pembrolizumab and surgery, they will be replaced.

## 7.6 Clinical Criteria for Early Trial Termination

Early trial termination will be the result of the criteria specified below:

- Quality or quantity of data recording is inaccurate or incomplete
- Poor adherence to protocol and regulatory requirements
- Incidence or severity of adverse drug reaction in this or other studies indicates a potential health hazard to subjects
- Plans to modify or discontinue the development of the study drug

In the event of Merck's decision to no longer supply study drug, ample notification will be provided so that appropriate adjustments to subject treatment can be made.

## 8.0 TRIAL FLOW CHART

### 8.1 Study Flow Chart

Table 5 - Schedule of Assessments

Evaluation	Screening (28-day Window)	Treatment Period				End of Treatment 	90-Day Follow-up 	Wound Care Follow-Up 	Survival Follow-up
		Week 1	Week 2	Week 4	Week 7				
Scheduling Window: ( $\pm$ 3 days unless otherwise specified)									
Informed Consent	X								
Inclusion/Exclusion Criteria	X								
Demographics and Medical History	X								
Prior and Concomitant Medication Review	X	X		X	X	X	X		
Pembrolizumab Administration 		X		X	X				
Radiation Therapy 			X	X	X				
Post-study anticancer therapy status							X	X	X
Survival Status 							X	X	X
Review Adverse Events		X		X	X	X	X	X	
Physical Examination (Including ECOG) 	X	X		X	X	X	X	X	
Vital Signs and Weight	X	X		X	X			X	
Pregnancy Test 	X	X		X	X	X			
PT/INR and aPTT	X						X		
CBC with Differential, Blood Chemistry	X	X		X	X	X	X		
Urinalysis	X	X							
T3, FT4 and TSH	X	X			X	X	X		
Tumor Imaging	X						X 		
Tumor tissue (biopsy) 	X						X 		
Correlative Studies Blood Collection		X		X	X	X	X		

This visit is to be completed 30 days ( $\pm$  14 days) after the last dose of pembrolizumab. This visit may be scheduled to coincide with the standard of care outpatient pre-operative surgical appointment. This visit must occur prior to any scheduled surgery.

This visit is to be completed 90 days ( $\pm$  14 days) after the last dose of pembrolizumab. This visit may be scheduled to coincide with the standard of care outpatient post-operative surgical appointment. This visit must be completed after any scheduled surgery.

This will be conducted 30 days ( $\pm$ 14 days) after the standard of care post-operative visit has been completed. If the 90-Day Follow-Up visit occurred within the  $\pm$  14 day window for this visit, this visit may be omitted.

Pembrolizumab may be administered with a window of  $\pm$ 3 days from Day 1 of each scheduled week for a maximum of three doses.

Given according to standard of care, beginning on Day 1 of Week 2 ( $\pm$  3 days). Exact duration of dosing dependent on standard of care radiation plan.

After the Wound Care Follow-Up Visit (or 90 Day Follow-Up Visit if the Wound Care Follow-Up visit is omitted), subjects will be contacted by telephone or medical record review every 12 weeks ( $\pm$  2 weeks) to assess for disease status, recurrence, and survival status until 1 year after initiation of pembrolizumab, death, withdrawal of consent, or the end of the study, whichever occurs first. After the first year, then subjects will be contacted via telephone or medical record review every 6 months ( $\pm$  2 months) to assess for disease status, recurrence, and survival status until 5 years after initiation of pembrolizumab, until death, withdrawal of consent, or the end of the study, whichever comes first.

Female subjects of child-bearing potential must have a negative serum pregnancy test at screening. Subsequent cycles may be either serum or urine tests. If more than 72 hours elapses between screening negative serum pregnancy assessment and C1D1, the negative serum pregnancy should be reconfirmed prior to administration of C1D1 treatment.

End of Treatment disease assessment via imaging must be completed within 3 weeks prior to planned surgery.

Archival tissue may be used instead of fresh biopsy collection. If archival tissue is utilized at baseline, tissue must have been collected within 90 days prior to planned Week 1 Day 1. End of treatment tissue will be collected from surgical resection. If no surgical resection occurs, this tissue will not be collected.

ECOG performance status must be confirmed within 7 days prior to the date of C1D1. If more than 7 days elapse between ECOG assessment and C1D1, the ECOG performance status should be reconfirmed prior to administration of C1D1 treatment.

## 9.0 TRIAL PROCEDURES

### 9.1 Trial Procedures

The Trial Flow Chart - Section 8.1 summarizes the trial procedures to be performed at each visit. Individual trial procedures are described in detail below. It may be necessary to perform these procedures at unscheduled time points if deemed clinically necessary by the treating investigator.

Furthermore, additional evaluations/testing may be deemed necessary by the Sponsor-Investigator and/or Merck for reasons related to subject safety. In some cases, such evaluation/testing may be potentially sensitive in nature (e.g., HIV, Hepatitis C, etc.), and thus local regulations may require that additional informed consent be obtained from the subject. In these cases, such evaluations/testing will be performed in accordance with those regulations.

### 9.2 Screening Evaluations

Each subject who enters into the screening period for the study receives a unique subject identification number before any study-related procedures are performed. The subject identification number will be assigned. This number will be used to identify the subject throughout the clinical study and must be used on all study documentation related to that subject.

The subject identification number must remain constant throughout the entire clinical study; it must not be changed after initial assignment, including if a subject is rescreened.

A signed and dated Institutional Review Board (IRB) approved informed consent form (latest approved version) must be obtained from each subject prior to performing any study-specific procedures. All subjects must personally sign and date the consent form before commencement of study-specific procedures. Adverse events are to be collected for a subject once they have signed the informed consent.

Screening evaluations will be performed for all subjects to determine study eligibility. These evaluations must be obtained  $\leq 28$  days prior to enrollment, unless otherwise indicated. Baseline imaging should be obtained as close to initiation of protocol therapy as possible.

The following procedures are to be completed during the 28-day screening period, after signed informed consent has been obtained, designated in the Study Flow Chart.

- Demographics (if allowed by local regulations, date of birth, sex, race, and ethnicity)
- Physical examination (including physical exam, medical/cancer history, ECOG performance status assessment)
- Prior/concomitant medications and procedures evaluation: all medications taken, and procedures completed within  $\leq 28$  days prior to signing of informed consent
- Vital signs (height [screening only], weight, temperature, sys/dias blood pressure, respiration rate, and pulse)

- Local Laboratory Assessments: blood chemistry, complete blood count (CBC) + differential, complete urinalysis with microscopic evaluation, serum pregnancy test (women of child-bearing potential), thyroid function, PT/INR and aPTT
- CT or MRI must be done within the 28-day screening period, but preferably should be done as close to enrollment as possible. CT/MRI may be used from prior to consent, as long as no more than 28 elapse days between imaging date and enrollment date.
- Tumor tissue biopsy or archival tissue (within 90 days of pembrolizumab treatment initiation)

A subject is considered enrolled when the treating investigator or Sponsor-Investigator decides that the subject has met all eligibility criteria. The investigator is to document this decision and date, in the subject's medical record and/or in/on the electronic case report form (eCRF). Subjects should initiate treatment within 7 days of being enrolled to the study (28-day screening window from date of consent to enrollment date, plus up to an additional 7 days from enrollment date to C1D1 [total elapsed time from initiating screening to initiating therapy may not exceed 35 days]).

